### **7.3.3 Removal of Subjects from Therapy or Assessment**

In accordance with the Declaration of Helsinki, subjects have the right to withdraw from the study at any time for any reason. The investigator and Ultragenyx also have the right to remove subjects from the study. Ultragenyx must be notified of all subject withdrawals as soon as possible. Ultragenyx also reserves the right to discontinue the study at any time for either clinical or administrative reasons and to discontinue participation of an individual subject or investigator due to poor enrollment or noncompliance, as applicable.

Subjects may be removed from the study for the following reasons:

- Occurrence of an unacceptable AE
- An illness that, in the judgment of the investigator or Ultragenyx, might place the subject at risk or invalidate the study
- Pregnancy in subject
- At the request of the subject, investigator, or Ultragenyx, for administrative or other reasons
- Protocol deviation or noncompliance

If the reason for removal of a subject from the study is an AE, the AE and any related test or procedure results will be recorded in the source documents and transcribed onto the Case Report Form (CRF). Each clinically significant abnormal laboratory value or other clinically meaningful abnormality should be followed until the abnormality resolves or until a decision is made that it is not likely to resolve. If such abnormalities do not return to normal within 30 days after the last dose given, their etiology should be identified and Ultragenyx should be notified. All unscheduled tests must be reported to Ultragenyx immediately.

If a subject discontinues from the study prematurely, every reasonable effort should be made to perform the Early Termination Visit procedures within four weeks of discontinuation. Subjects who discontinue due to SAE will be monitored for safety through the final Safety Follow-up TC (as defined in Section 7.4.3.1).

#### **7.3.3.1 Stopping Rules**

No formal statistical stopping criteria will be applied for this study. A Data Monitoring Committee (DMC) will be constituted for Studies UX023-CL303 and UX023-CL304 and will act in an advisory capacity to monitor the safety of KRN23 on a routine basis until the end of the Treatment Period (Week 48) (Section 7.6.7). The DMC may provide advice to Ultragenyx to aid in the determination of whether study enrollment should be paused or if the study should be stopped. If the Sponsor deems it appropriate to restart the trial following an internal safety review, this will be done only following approval by Regulatory Authorities.

During Treatment Extension Periods I and II, safety data will be reviewed by the Ultragenyx Study Safety Review Team (SSRT) as described in Section 8.5.4.6.

Individual subjects who experience any unexpected and possibly, probably, or definitely drug-related SAEs (Section 8.5.3) that represent a change in the nature or an increase in frequency of the serious event from their prior medical history will be assessed as to whether the subject will continue on the study.

Individual subjects will be monitored for ectopic mineralization (Section 7.5.3). If new or clinically significant worsening in mineralization is considered clinically meaningful by the investigator and/or sponsor and related to study drug, the subject will be discontinued from the study.

Regulatory Authorities, as well as the Institutional Review Board (IRB)/Ethics Committee (EC) will be informed should unexpected and possibly, probably, or definitely drug-related SAEs occur. A full clinical evaluation of the event will be performed in order to make a decision regarding what actions to take, including whether to recommend stopping the study. Regulatory Authorities, as well as IRBs/ECs, will be informed if the study is paused or stopped.

## 7.4 Treatments

The study drug is manufactured, packaged, and labeled according to Good Manufacturing Practice (GMP) regulations. The Investigational Product should be securely stored under conditions indicated in the IB.

### 7.4.1 Investigational Product

KRN23 is a sterile, clear, colorless, and preservative-free solution supplied in single-use 5-mL vials containing 1 mL of KRN23 at a concentration of 30 mg/mL. KRN23 will be administered without dilution. All subjects will receive 1.0 mg/kg KRN23 monthly (Q4W, 28 days), rounded to the nearest 10 mg. The amount of drug administered will be calculated based on baseline weight and a 1.0 mg/kg KRN23 dose level (rounded to the nearest 10 mg) up to a maximum dose of 90 mg. The dose will remain fixed for the duration of the study, provided serum phosphorous levels do not exceed 5.0 mg/dL (1.61 mmol/L) at any time or 4.5 mg/dL (1.45 mmol/L) on two occasions. The dose will be recalculated if body weight changes by more than 20% from the baseline measurement.

Subjects will receive study drug via SC injection to the abdomen, upper arms, or thighs; the injection site will be rotated with each injection. No more than 1.5 mL may be administered to a single injection site. If the dose requires more than 1.5 mL, multiple injections must be administered, each at a different injection site.

If serum phosphorus increases above 5.0 mg/dL (1.61 mmol/L) at any time the actual dose will be decreased by half. If serum phosphorous increases above the ULN (4.5 mg/dL; 1.45 mmol/L) but does not exceed 5.0 mg/dL (1.61 mmol/L), the dose will be adjusted only

if a second serum phosphorus result exceeds the ULN. Following a downward dose adjustment, the investigator together with the medical monitor should determine how and when to dose titrate up. Unscheduled serum phosphorus assessments may be necessary. Based on the totality of the data from studies INT-001 and INT-002 over a period of 16 months in which most subjects were treated with 1.0 mg/kg KRN23 and no subject experienced an elevation of serum phosphorus that approached the 4.5 mg/dL (1.45 mmol/L) threshold, it is considered unlikely that dose adjustment will be necessary.

Refer to the Study Reference Manual for additional information on dose adjustments.

#### **7.4.2 Reference Therapy**

The study is a single-arm, open-label study. All subjects will be on active treatment; no reference therapy or placebo will be administered.

#### **7.4.3 Selection of Doses and Study Duration**

The goal of therapy in adults with XLH is to increase serum phosphorus sufficiently to allow the bone to fully mineralize, and thereby improve bone physiology, structure, and function. The level of serum phosphorus needed to restore bone metabolism homeostasis and mineralization is not precisely known, but there is a general agreement that increasing serum phosphorus above the lower limit of normal (LLN) is an appropriate strategy. Another key consideration of the therapeutic goal is related to the safety concerns associated with ectopic mineralization, in particular nephrocalcinosis. The risk of nephrocalcinosis with the current oral phosphorus and active vitamin D therapy increases with higher doses, and is believed to be associated with exacerbated oral phosphate wasting in the urine, and secondary hypercalciuria (Goodyer et al. 1987), (Verge et al. 1991), (Sabbagh et al. 2008). Although mechanistically KRN23 does not increase urinary phosphorus or calcium, the dosing strategy will be conservative, aiming to maintain serum phosphorus above the LLN for the majority of a given dose interval without causing hyperphosphatemia.

The Phase 3 dose is based on PK, PD, clinical, and safety data obtained in previous studies (KRN23-US-02, KRN23-INT-001 and KRN23-INT-002). These studies indicate normalization of serum phosphorus levels occurs with SC KRN23 doses ranging from 0.3 to 1.0 mg/dL Q4W. The safety data showed repeated monthly doses up to 1.0 mg/kg were well tolerated by adult subjects with XLH.

Data from KRN23-INT-002, the longest clinical study to date, is the primary basis of the dosing strategy. All subjects in the study responded to KRN23 at doses of 0.3, 0.6, and 1.0 mg/kg by increasing serum phosphorus. After the initial dose-titration period, the majority of subjects (60% to 74%) stabilized on an optimal dose of 1.0 mg/kg KRN23 and achieved serum phosphorus levels within the normal range. The maximum increase in serum phosphorus following KRN23 administration was approximately 1 mg/dL from baseline. No hyperphosphatemia (>4.5 mg/dL; 1.45 mmol/L) was detected at any time point. Increases in serum phosphorus persisted through much of each treatment interval and

throughout the 12 months of treatment; however, serum phosphorus decreased towards the end of each dose interval as KRN23 concentrations waned. Importantly, KRN23 administration increased serum phosphorus without negatively affecting other parameters such as iPTH and calcium.

Based on these data, a KRN23 dose of 1.0 mg/kg (rounded to the nearest 10 mg) administered Q4W by the SC route was selected as the dose and regimen expected to be therapeutic while maintaining a reasonable safety margin.

#### **7.4.3.1 Study Duration**

The planned duration of treatment in this study is 96 weeks for subjects at sites outside of the US or up to approximately 141 weeks, until end of September 2018, for subjects at sites in the US, or until one of the following occurs: the subject withdraws consent, the subject is discontinued from the study at the discretion of the investigator or Ultragenyx, or the study is terminated. The length of the study is intended to define whether KRN23 is effective at reducing excess osteoid after 48 weeks. Subjects who complete the Open-Label Treatment Period will continue to receive KRN23 for an additional 48 weeks during Treatment Extension Period I. Subjects at study sites outside the US will have their EOS efficacy visit (ie, EOS I) at the end of this period. Subjects at US sites will continue KRN23 treatment for up to an additional approximately 45 weeks in Treatment Extension Period II. The duration of Treatment Extension Period II may vary for individual subjects. For each subject who participates in this period, the study site will schedule the EOS efficacy visit (ie, EOS II) to take place before 30 September 2018. The duration of the period will be determined by the time from the start of Week 97 through the EOS II Visit.

For subjects not immediately continuing KRN23 treatment under commercial use or another mechanism upon completion of study drug treatment or early withdrawal from this study, a Safety Follow-up TC will occur 4 weeks (+ 5 days) after their final study site visit (ie, EOS I [non-US subjects], EOS II [US subjects], or ET Visit) to collect information on whether KRN23 treatment has been started through another mechanism and, if not, any ongoing or new AEs, SAEs, or concomitant medications. If the subject is not continuing KRN23 therapy under commercial use or another mechanism at that time, an additional Safety Follow-up TC will occur 8 weeks (+ 5 days) after the subject's final study site visit to collect information on whether KRN23 treatment has been started through another mechanism and, if not, any ongoing or new AEs, SAEs, or concomitant medications.

The end of the study is defined as the last day that protocol-specified assessments (including telephone contact) are conducted for the last subject. The maximum planned study duration (treatment plus safety follow-up) is approximately 149 weeks.

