KRN23 will be administered via SC injections monthly (Q4W, 28 days) for 48 weeks. Subjects will then continue into an additional 48-week Treatment Extension Period I (until Week 96). For subjects at study sites outside of the United States (US), the Week 96 Visit will be their End of Study (EOS) efficacy visit (referred to as EOS I). For subjects at sites in the US, treatment will continue for up to an additional 45 weeks in an open-label Treatment Extension Period II, until end of September 2018, at which time they will have their EOS efficacy visit (referred to as EOS II). (The duration of this period will vary for individual subjects and will be determined by the time from the start of Week 97 through their EOS II Visit). For subjects not immediately continuing KRN23 treatment under commercial use or another mechanism upon completion of study drug treatment or early withdrawal from this study, a Safety Follow-up telephone call (TC) will occur 4 weeks (+5 days) after the subject's final study site visit (ie EOS I [non-US subjects], EOS II [US subjects], or Early Termination [ET] visit) to collect information on any ongoing or new AEs, SAEs, and concomitant medications. If the subject is not continuing KRN23 therapy under commercial use or another mechanism at that time, an additional Safety Follow-up TC will occur at 8 weeks (+ 5 days) after the subject's final study site visit. The end of this study is defined as the last day that the protocol specified assessments (including telephone contact) are conducted for the last subject..

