For subjects not immediately continuing KRN23 treatment under commercial use or another mechanism upon completion of study drug treatment or early withdrawal from this study, a Safety Follow-up TC will occur 4 weeks (+5 days) after their final study site visit (ie, EOS I [non-US subjects], EOS II [US subjects], or ET Visit) to collect information on whether KRN23 treatment has been started through another mechanism and, if not, any ongoing or new AEs, SAEs, or concomitant medications. If the subject is not continuing KRN23 therapy under commercial use or another mechanism at that time, then site personnel will initiate a subsequent Safety Follow-up TC 8 weeks (+ 5 days) after the subject's final study site visit to collect information on whether KRN23 treatment has been started through another mechanism and, if not, any ongoing or new AEs, SAEs, or concomitant medications.

The schedule of visits and assessments conducted during Screening and Baseline, and the Open-Label Treatment Period are provided in [Table 2.1](#) and [Table 2.2](#). The schedule of visits and assessments conducted during the Treatment Extension Periods I and II are provided in [Table 2.3](#) and [Table 2.4](#). Refer to the Study Reference Manual for additional details and a recommended schedule and order of specific assessments.

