#### **7.5.3.11 Adverse Events**

All AEs will be recorded from the time the subject signs the informed consent through the final Safety Follow-up TC (as defined in Section 7.4.3.1). The determination, evaluation, reporting, and follow-up of AEs will be performed as outlined in Section 8.5. At each visit, subjects will be asked about any new or ongoing AEs since the previous visit. Assessments of AEs will occur at each visit to the investigational site and at all Home Health Visits.

Clinically significant changes from baseline in physical examination findings, vital signs, weight, clinical laboratory parameters, renal ultrasounds, eGFR, ECHO and ECGs will be recorded as AEs or SAEs, if deemed appropriate by the investigator.

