### 8.5.4 Adverse Event Reporting to Ultragenyx

#### 8.5.4.1 General

All AEs (i.e. any new or worsening in severity or frequency of a preexisting condition) with onset after the subject signs consent for study participation must be promptly documented on the AE eCRF via the EDC system. The Principal Investigator is responsible for evaluating all AEs, obtaining supporting documents, and ensuring documentation of the event is adequate. Details of the AE must include severity, relationship to study drug, duration, and outcome.

All AEs will be collected from the time the subject signs informed consent through the final Safety Follow-up TC (as defined in Section 7.4.3.1). In addition, the Investigator should report any AE that occurs after this time period that is believed to have a reasonable possibility of being associated with study drug.

AEs ongoing at the final Safety Follow-up TC should have a comment in the source document by the Investigator whether the event has recovered, recovered with sequelae, or stabilized.

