#### **8.5.4.2 Serious Adverse Events, Serious Adverse Drug Reactions, and Requirements for Immediate Reporting**

Any SAE that occurs at any time during the study, including a clinically significantly abnormal laboratory test result that is considered serious, must be reported within 24 hours of knowledge of the event to Ultragenyx or its designee. These requirements apply equally to all subjects, regardless of the study phase or the at-risk subject's treatment assignment or dosage. The reporting requirement for SAEs is from the time of signing of the ICF through the final Safety Follow-up TC.

SAEs will be reported by completing and submitting SAE report forms to Ultragenyx or its designee. Initial SAE reports must be followed by detailed descriptions. These should include copies of hospital case records and other documents when requested. Telephone reports must be confirmed promptly by facsimile. Follow-up SAE information must be submitted in a timely manner as additional information becomes available. All SAEs regardless of relationship to study drug must be followed to resolution or stabilization if improvement is not expected.

A death occurring during the study, during the per-protocol follow-up period, or through the final Safety Follow-up TC (as defined in Section 7.4.3.1) must be reported to Ultragenyx or its designee within 24 hours of knowledge of the death whether or not it is considered treatment-related.

The investigator also must notify the IRB/EC of the occurrence of the SAE, in writing, as soon as is practicable and in accordance with IRB/EC requirements and local law. A copy of this notification must be provided to Ultragenyx or its designee.

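### The safety follow-up calls ask about adverse events only if KRN23 has not been restarted elsewhere, which conflicts with the protocol's own AE and SAE collection period

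*Protocol*

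**What the plan says.** The calls apply to subjects who do not move straight on to KRN23 from another source after EOS I, EOS II or early termination. Under Protocol 7.4.3.1, "a Safety Follow-up TC will occur 4 weeks (+ 5 days) after their final study site visit". If KRN23 has not been resumed by then, "an additional Safety Follow-up TC will occur 8 weeks (+ 5 days) after the subject's final study site visit".

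On content, the protocol gives two versions.

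- **Conditional.** Section 7.4.3.1 has both calls find out "whether KRN23 treatment has been started through another mechanism and, if not, any ongoing or new AEs, SAEs, or concomitant medications". Section 7.5 repeats this ("to collect information on whether KRN23 treatment has been started through another mechanism and, if not, any ongoing or new AEs, SAEs, or concomitant medications"), as do footnote 18 to Table 2.3 and footnote 13 to Table 2.4.
- **Unconditional.** Section 7.1 says the 4-week call is made "to collect information on any ongoing or new AEs, SAEs, and concomitant medications". The synopsis says the same. Neither states the content of the 8-week call.

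The collection period is set separately, without any carve-out for restarters:

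- Section 7.5.3.11: "All AEs will be recorded from the time the subject signs the informed consent through the final Safety Follow-up TC (as defined in Section 7.4.3.1".
- Section 8.5.4.1: "All AEs will be collected from the time the subject signs informed consent through the final Safety Follow-up TC (as defined in Section 7.4.3.1".
- Section 8.5.4.2: "The reporting requirement for SAEs is from the time of signing of the ICF through the final Safety Follow-up TC".

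**The concern.** The calls cover the time after the last site visit when a subject is off KRN23. The Amendment 3 rationale, cited here only for intent, gives exactly that interval as the reason for adding them. Under the conditional wording, the interval goes unasked for any subject who restarts before the call: the site hears that KRN23 has been restarted, and the AE, SAE and medication questions do not follow. A wish to keep events on non-study supply out of the study data would be understandable, but the condition also leaves out the off-drug events that came before the restart.

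At stake is the consistency of the safety data after treatment ends. Two sites with identical subjects could follow different sections and collect different data, each in line with the protocol.

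**Working it through.** **1. The plan's own figure.** Treatment weeks from Sections 7.2 and 7.4.3.1: 48 + 48 + 45 = 141. Adding 8 weeks to the second call: 141 + 8 = 149, which reproduces the maximum duration in Section 7.4.3.1. No later contact is planned after the 8-week call.

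**2. Call windows, in days after the final site visit.**

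- Call 1: 4 × 7 = 28, and 28 + 5 = 33, so days 28 to 33.
- Call 2: 8 × 7 = 56, and 56 + 5 = 61, so days 56 to 61.

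**3. What each place requires for a subject who has restarted.**

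| Place | AEs and SAEs before the restart |
|---|---|
| 7.4.3.1; 7.5; Table 2.3 footnote 18; Table 2.4 footnote 13 | Not asked |
| Synopsis; 7.1 (4-week call) | Asked |
| 7.5.3.11; 8.5.4.1 (all AEs); 8.5.4.2 (SAEs) | Required through the final call |

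Sections 7.5.3.11 and 8.5.4.1 send the reader to 7.4.3.1 for the definition of the final call, so the collection rule depends on the section that contains the condition. Neither they nor 8.5.4.2 mention concomitant medications. On medications, the conflict is with the synopsis and 7.1 only.

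**4. Restart before call 1.** Call 2 is not held, so call 1 is the final call. Collection is required through it, but no AE question is put. The unprompted time runs from day 0 to the call, at most 33 days.

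**5. Restart between the calls.** Call 1 covered the time before it. The unprompted time runs from call 1 to call 2: shortest 56 − 33 = 23 days, longest 61 − 28 = 33 days.

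Cases 4 and 5 exclude each other for a given subject, so the maximum is about 33 days. The off-drug part of it is shorter, because it ends at the restart.

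**6. Would a cut-off at the restart date, written only into the four conditional places, be enough?** Take a restart on day 21 (illustrative). The call on day 28 to 33 would then ask about days 0 to 21. Sections 7.5.3.11, 8.5.4.1 and 8.5.4.2 would still require the remaining 28 − 21 = 7 to 33 − 21 = 12 days. The conflict would be smaller but not resolved.

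**7. Other scheduled contact.** Section 7.5.3.11 places AE questioning at site and home health visits. Tables 2.3 and 2.4 show nothing but the calls after EOS or ET, so no other scheduled contact supplies the question.

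**8. The SAP.** Version 1.0 covers the protocol to Amendment 2 and describes a single call 12 weeks after the last dose, so it does not settle the point. Its TEAE definition (8.8.2) has no end date, so events in this interval would be counted if collected.

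**The case against.** The strongest reply is that reporting duties do not depend on the call text. Section 8.5.4.1 requires all AEs through the final call and asks for later ones that may plausibly be linked to study drug. Section 8.5.4.2 requires SAEs within 24 hours of the site learning of them and has its own rule for deaths. The footnotes require follow-up until safety concerns are resolved. This stands: a volunteered event, or one already under follow-up, is still reportable. It narrows the point to the missing prompt for new events; it does not reconcile the sections.

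It is also fair to say that completers have some AE collection after their last dose without the calls. Non-US subjects are last dosed at Week 92 and have AEs collected at Weeks 94 and 96, which is (96 − 92) × 7 = 28 days. For them call 1 falls 28 + 28 = 56 to 28 + 33 = 61 days after that dose. EOS II also collects AEs with no dose scheduled. The safety objective in Section 6 names no post-dose window. So the gap concerns the end of a long follow-up.

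A reader might infer more, and the documents do not support it:

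- **That events are lost.** Only the prompt is missing.
- **That the two 33-day figures add up.** They are alternatives for any one subject.
- **That the loss is non-random and differs between US and non-US subjects.** The Amendment 3 rationale says supply routes differ, but nothing gives restart timing by region or ties restart to AE risk.
- **That one missed SAE can be put as a share of the roughly 14 subjects to size the problem.** No restart count is given, and such a figure presumes that an SAE goes unreported despite the 24-hour duty.

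**Conclusion.** The point holds as an internal contradiction about what the follow-up calls collect. Four places make AE, SAE and medication collection depend on KRN23 not having been restarted. Three sections require AEs or SAEs through the final call without exception, and two describe the 4-week call without the condition. Because the condition appears in four places, including the schedule footnotes, it is not an isolated slip.

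The effect is that a restarter is not prompted about new events over at most about 33 days. This assumes that sites follow the call wording literally and that the calls fall within their stated windows. The number of subjects concerned is unknown. Subjects who continue KRN23 immediately receive no call and are outside the point. No efficacy endpoint or analysis is affected.

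**What to change.** Remove the restart condition from Section 7.4.3.1, Section 7.5, footnote 18 to Table 2.3 and footnote 13 to Table 2.4. Each call should record the restart date, if any, and ask about all AEs, SAEs and concomitant medications from the last study contact through the call. For AEs and SAEs this is what 7.5.3.11, 8.5.4.1 and 8.5.4.2 already require. For medications it follows the synopsis and 7.1. With the restart date recorded, events before and after restart can be separated in the analysis.

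If the sponsor prefers collection to end at the restart date, that cut-off should be stated in the four places and also in 7.5.3.11, 8.5.4.1, 8.5.4.2, the synopsis and 7.1, so that all agree.

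The cost is a few sentences at the next amendment and, if the CRF lacks one, a field for the restart date. The calls already take place; each would take a few minutes longer.
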